1.0 Study Summary

Study Title	A PILOT STUDY TO DETERMINE THE FEASIBILITY OF A COUPLES' ORIENTED INTERVENTION TO PROMOTE CPAP ADHERENCE AMONG AFRICAN AMERICAN PATIENTS WITH OBSTRUCTIVE SLEEP APNEA
Study Design	Randomized Controlled Trial
Primary Objective	Mean CPAP adherence at 90 days
Secondary Objective(s)	Mean CPAP adherence at 30 days Change in mean CPAP adherence at 90 days (compared to baseline) Self-efficacy to use CPAP Patient and bed partner quality of life Patient and bed partner quality of sleep
Research Intervention(s)/ Investigational Agent(s)	Peer motivators Behavioral couple therapy Telemonitoring and feedback
IND/IDE #	N/A
Study Population	African American patients with OSA and bed partner
Sample Size	20 patients and 20 bed partners
Study Duration for individual participants	90 days
Study Specific Abbreviations/ Definitions	OSA Obstructive Sleep Apnea CPAP Continuous Positive Airway Pressure

2.0 Background and Objectives

Obstructive sleep apnea (OSA), which affects 26% of adults over age 30 in the US¹ and over 900 million people worldwide², is a disorder of sleep that results from intermittent complete or partial airway collapse and leads to episodes of apnea, hypopnea, and arousal from sleep.^{3,4} Without treatment, OSA is associated with both immediate and long term adverse health outcomes, including motor vehicle accidents, hypertension,⁵ and coronary artery disease.⁶ African Americans are more likely to develop OSA and its complications despite presenting with similar symptoms.⁷⁻⁹ Continuous positive airway pressure (CPAP) is efficacious in treating moderate to severe OSA¹⁰⁻¹² and in preventing many of its complications. However, CPAP adherence is low among African Americans.

In our prior work, we found that untreated OSA can also adversely affect the sleep and daytime functioning of bed partners by preventing them from having continuous, restful sleep.^{13,14} Partners' sleep loss often results in frustration, exhaustion, interference with work, and a strained relationship. In contrast, OSA treatment improves bed partner sleep quality and may improve intimate relationships.¹⁵ Perceived partner support is associated with more CPAP use.¹⁴ Few studies, however, have examined the efficacy of bed partner interventions in improving OSA outcomes.

We propose to pilot test a couple-oriented intervention in a randomized controlled trial of 20 African American patients diagnosed with moderate to severe OSA and their partners. Half of the patients will receive optimal **usual care currently implemented at MetroHealth**, consisting of sleep therapist-initiated standardized education about OSA, sleep hygiene, and CPAP use; personalized mask fittings; and follow-up at 1 week to troubleshoot problems with CPAP utilization. Participants will follow up with their sleep providers per usual. The remaining patients and their bed partners will receive a **couple-oriented intervention** consisting of guideline-recommended best practices for improving CPAP adherence consisting of sleep therapist-initiated **standardized education for couples** about OSA, sleep hygiene, and CPAP use; personalized mask fittings; and follow-up at 1 week to troubleshoot problems with CPAP utilization. Couples will participate in two couple-oriented support groups led by an African American patient with long standing OSA treated with CPAP and their partner. Patients and partners will receive tailored text messages encouraging adherence. In addition, **couples will receive** five 60-minute **virtual cognitive behavioral couple therapy** sessions with a health psychologist trained in behavioral sleep medicine that will focus on enhancing **couples' knowledge** of CPAP, **patients' self-efficacy** to use CPAP, **couple's relationship dynamics**, and **partners' skill and self-efficacy** in assisting the patient with CPAP adherence.

Primary Aim 1: To determine the impact of a couple-oriented intervention on CPAP adherence.

Hypothesis: Compared to usual care patients, patients who receive the couple-oriented intervention will use CPAP for more hours per night over 90 days (primary outcome).

Primary Aim 2: To determine the impact of a couples-oriented intervention on quality of sleep, functional status, and quality of life of OSA patients and their partners.

Hypothesis: Compared to usual care couples, couples who receive the couple-oriented intervention will have a higher quality of sleep, functional status, and quality of life at 90 days (secondary outcomes).

3.0 Background

3.01 Many Americans have obstructive sleep apnea (OSA).

Obstructive sleep apnea (OSA) affects 13% of adult men and 6% of adult women in the US.¹ OSA occurs when the upper airway intermittently narrows or completely closes during sleep, resulting in complete or near cessation of breathing for at least 10 seconds at a time.¹⁶ Oscillations in oxygen saturation are common and may fall dangerously low. Snoring may be loud and disruptive to others. These respiratory events cease when the patient partially arouses. Partial arousals almost never cause the person to wake completely, but significantly decrease the likelihood of obtaining continuous sleep. As a result, OSA is often first recognized by bed partners who encourage the patient to seek medical care.¹⁷

3.02 OSA is a cause of significant morbidity and mortality.

Untreated OSA is associated with motor vehicle accidents and occupational injuries.^{18,19} Over time, the cardiovascular system may become affected leading to the development of hypertension,⁵ coronary artery disease,^{6,20} atrial fibrillation,²¹ and sudden cardiac death.²² OSA is also associated with the development of ischemic stroke.²³ The all-cause mortality hazard ratio for untreated OSA compared to no OSA is 3.8 (95% CI 1.6 – 9) after adjustment for age, sex, body mass index (BMI), and other factors.²⁴

3.02 African Americans are at increased risk of being adversely affected by OSA.

Meta-analyses have found African Americans to have worse subjective and objective sleep and to be at increased risk of developing OSA compared to whites.^{25,26} Studies have found a higher severity of OSA among African Americans compared to whites as well as an increase in OSA-related complications. For example, in the Multi-Ethnic Study of Atherosclerosis (MESA), African Americans with an increased risk of OSA had a higher prevalence of inflammatory mediators and cardiovascular risk factors compared to other racial and ethnic groups.^{27,28}

3.03 Continuous Positive Airway Pressure (CPAP) treats moderate and severe OSA.

CPAP effectively treats OSA by providing a pneumatic splint preventing airway collapse during sleep.^{10–12} It is associated with improvements in quality of life,^{29–32} and reductions in morbidity.^{33–37} By reversing snoring and sleep disruption, CPAP also improves sleep quality among bed partners.^{29,38} There is no threshold duration of use for optimal benefit from CPAP suggesting a linear improvement in outcomes with use. While use for more than 4 hours/night improves sleepiness and is considered the gold standard duration,³⁹ more than 5 hours/night of use improves blood pressure⁴⁰ and lowers the risk for weight gain.⁴¹ More than 6 hours/night of use improves memory and daily functioning.⁴²

3.04 CPAP adherence is low, particularly among African Americans.

Only about 50% of patients with OSA use CPAP for more than 4 hours per night.⁴² African Americans and patients of lower socioeconomic position have lower adherence compared to whites and patients of high socioeconomic position even when adjusting for its cost.^{43–45} Patient adherence soon after CPAP initiation is associated with long-term adherence.⁴⁶ There are differences in symptom recognition, risk perception, and outcome expectations between patients who adhere to CPAP and those who do not.⁴⁷

3.05 Individual interventions to improve CPAP adherence have had modest results.

Multiple studies have examined the impact of different interventions on CPAP adherence with negative or moderately positive results.^{48–55} A recent systematic review categorized the

interventions to determine which had the greatest impact on CPAP adherence.⁵⁶

Troubleshooting interventions increased CPAP usage by approximately 40 minutes/night, and educational interventions increased CPAP usage by about 50 minutes/night. Behavioral therapy interventions had the largest effect with an increase of 1.31 hours/night. However, the quality of the evidence was rated as low. Guidelines encourage use of **multifaceted interventions that combine educational interventions at CPAP initiation with troubleshooting and behavioral interventions during the initial period of accommodating to CPAP** to maximize adherence.⁵⁷ In addition, telemonitoring is recommended for early identification and intervention among those who are non-adherent. There have been few studies that tested interventions among African American patients to specifically address sleep health disparities.^{58,59}

2.07 Bed partners may be an integral component of OSA adherence.

Randomized trials demonstrate CPAP therapy improves sleepiness and quality of life not only in patients, but also their bed partners.^{60,61} Thus, a couple-based intervention may improve both the patient's OSA and the adverse effects of OSA on the bed partner.⁶² A qualitative study of 20 couples by our group identified several facilitators of CPAP use, including couples working together to use CPAP, perceived benefit of CPAP to both partners, patients motivated to use CPAP for the benefit of partners, and partner support to encourage CPAP use.⁶³ Barriers to use included bothersome equipment causing disruptions in sleep and bedtime routine, interruptions to intimacy, and concern about a change in body image while wearing CPAP. Sawyer identified daily interactions with the partner providing support, assistance with troubleshooting, and observing positive response to CPAP in the patient as positive influences on patients' commitments to CPAP.⁴⁷

2.08 Cognitive behavioral couple therapy (CBCT) may improve OSA adherence.

Cognitive behavioral couple therapy (CBCT) integrates behavioral couple and cognitive therapy to improve communication, problem-solving, and relationship quality among couples.⁶⁴ CBCT focuses on the role of dysfunctional attitudes and attributions on each partner's cognitions, behaviors, and emotional responses. Specifically, CBCT assists couples by restructuring cognitions that bring in relational distress through unrealistic expectations, irrational beliefs, and dysfunctional assumptions. Effectiveness studies of CBCT showed improved relationship satisfaction, communication, and problem-solving skills among couples.⁶⁵ Studies using the CBCT approach with patients suffering from PTSD, OCD, vestibulodynia, and cancer, found positive improvement in couples' relationships and relationship satisfaction.^{64,66,67}

CBCT has been used previously among OSA patients. In Australia, CBCT was associated with a 2.9-hour improvement in CPAP adherence.⁴⁸ Because cognitive behavioral therapy is the gold standard for insomnia management, the expertise delivering this treatment already exists in most sleep medicine clinics. It should therefore not be difficult for providers to implement CBCT into their OSA management.

2.09 Preliminary work: African American patients with OSA and their partners are receptive to remote intervention

We conducted Zoom interviews with 15 African American patients with OSA and their 15 partners to determine their unique needs regarding OSA management and to determine their willingness to receive the intervention remotely. Couples were excited about having a remotely administered couples-oriented intervention to improve OSA management. One patient commented, "It's really helpful if the person knows you're saving your spouse's life. So yeah, I

think they should be involved.” Another stated, “She encourages me, and she’s another reason why I wear my CPAP.” Couples also suggested that African American couples with experience in dealing with OSA and CPAP interact with newly diagnosed patients and their partners to help them understand what to expect and how to address problems that arise. One patient stated, “When you first start using the machine, it’s going to be uncomfortable.” Another said, “Just hearing about the issues... Just even talking like ‘Hey, this is normal’.” These findings were used to develop our couple-oriented intervention for African Americans.

2.10 Innovative features of proposed trial

Previous studies of CPAP adherence have had little or no involvement of bed partners, short follow up durations, small sample sizes, and single interventions. Furthermore, African American participation has been extremely limited. There are several unique features that distinguish this project from prior work. First, we will recruit African American participants using a similar approach to that used to successfully recruit participants in our prior work. Second, we will incorporate bed partners into the intervention. Third, our intervention is built on feedback received from African American patients and their bed partners. Fourth, African American couples with personal experience with OSA will serve as peer motivators. The use of peer motivators looks promising.^{68,69} Fifth, rather than testing single interventions, we propose a multi-modality intervention that combines education, troubleshooting, peer motivators, continuous telemonitoring, and remote feedback of CPAP use, each of which in isolation have been suggested to modestly improve CPAP adherence.

4.0 Study Endpoints

Primary Endpoint: Mean CPAP adherence over 90 days

Secondary Endpoints: Mean CPAP adherence over 30 days
Patient and Bedpartner quality of sleep at 90 days
Patient and Bedpartner functional status at 90 days
Patient and Bedpartner quality of life at 90 days

5.0 Study Intervention/Investigational Agent

5.01 Usual care arm

Patients in the usual care arm will receive standard of care in the management of OSA. Patients will receive care from their sleep provider per usual. MyChart, the patient portal of the electronic health record, will be used to send patients a link to user-friendly OSA patient education programs (Emmi; Emmi Solutions LLC.).⁵³ Within 1 week of being diagnosed with OSA and enrolled in the study, sleep technologists will meet in person with patients and provide them with their auto-titrating CPAP machine; train them on its use, upkeep, and troubleshooting; and perform personalized mask fittings. Patients will be informed that their CPAP adherence will be monitored. Every morning, CPAP adherence data will be uploaded to RedCap. Patients with CPAP technical difficulties will be encouraged to contact the sleep technologist for assistance. Patients will attend a 90-minute virtual webinar and question-answer session on hypertension management, cancer screening, or weight management at 1 and 3 months led by African American physicians with expertise in each topic.

5.01a Virtual sleep logs as ecological momentary assessments. Patients will be asked whether they would prefer to receive communications via telephone, email, text message, or a

combination. During the first 6 months of the study, patients and bed partners will receive up to 4 interactive text messages/week in the morning inquiring about the quality of their sleep, their sleep-wake patterns, symptoms attributable to OSA, perceptions regarding OSA and CPAP, what time they went to sleep, when they woke up for the final time, how they rated the quality of their sleep, and any additional comments they may have.^{70,71}

5.02 Couple-oriented intervention arm

5.02a Peer-Motivator Couples. Patients in the couple-oriented intervention arm will also receive usual care. However, the health-related virtual webinars at 1 and 3 months will be replaced by OSA virtual support groups led by an African American patient with long-standing OSA and their bed partner. Peer-motivator couples will be trained and certified as competent prior to interacting with study participants. They will share their experiences with managing OSA including coping strategies to maximize CPAP adherence.

5.02b Telemonitoring. Physiologic and adherence data from patients' CPAP machines will be uploaded into RedCap and used to automatically trigger messages of encouragement to patients and partners. For the first three days following receipt of CPAP, patients and bed partners will each receive text messages regarding CPAP use for the previous night. Similar messages will be received after the first study week with 3 nights of consecutive use (or lack of use). No more than 4 messages will be sent per week to prevent respondent fatigue. Example messages include:

Trigger	Patient Message	Bed Partner Message
CPAP use < 4 hours per night in any of the first 3 nights of the study	Did you have any difficulty using CPAP last night? What changes can you make to increase your use tonight?	Did your partner had trouble using CPAP last night? How can you help them use it tonight?
CPAP use > 4 hours per night in any of the first 3 nights of the study	Congratulations on wearing your CPAP last night. Let's see if you can do it again tonight!	Your partner was able to wear their CPAP tonight. How can you help them to use it again tonight?
CPAP use < 4 hour per night for 3 consecutive nights (first occurrence)	It takes some time to get use to CPAP. However, regular use can improve your sleepiness and your wellbeing. Can you try again tonight?	Your partner has not reached their CPAP goal for the last 3 nights. What are some ways to help them use it tonight?
CPAP use > 4 hours per night for 3 consecutive nights (first occurrence)	Way to reach your sleep goal 3 nights in a row! Can you do it again tonight?	Your partner has reached their CPAP goal 3 nights in a row! Can you encourage them again tonight?

5.02c Cognitive Behavioral Couple Therapy (CBCT). A psychologist will facilitate two virtual 60-minute CBCT sessions. Virtual psychotherapy for couples is both efficacious and feasible.⁷² The therapy process will be based on the principles of psychology and chronic illness, the reciprocal association between the couple's functioning and the issues related to OSA.⁷³ These sessions will consist of four main components: problem-solving training, communication training, cognitive restructuring, and functional structuring of the couple's relationship. [name] will have a not-guiding stance towards a preconceived thought but will facilitate open exploration and problem solving.

Each session will begin with review of assigned tasks from the prior session. Couples and therapist will review the digital sleep logs and CPAP adherence data. They will then problem-solve ways to improve CPAP adherence. [name] will use guided discovery with Socratic questioning to facilitate couples' exploration of automatic thoughts, emotions, assumptions, and beliefs. Behavioral experiments will be used to help couples test the validity of their cognitions and beliefs and to promote awareness of the way they perceive and react to events and to each other. Couples will be encouraged to continue the experiments in their daily lives outside of the sessions. Sessions will conclude with assigned homework to be completed by the couple prior to the subsequent session. Prior to ending the session, couples will be asked to comment on whether they received the help they needed for that day and whether they felt fully understood. The final session will have discussion of the positive effects resulting from having OSA (benefit finding), a review of the progress made in therapy, and the challenges that lie ahead.

SESSION	SESSION GOALS
1 ⁷⁴	
 -Introduction to cognitive behavioral couples' therapy -Review of goals of therapy -Collaborative setting of agenda by therapist and couple -Discuss baseline digital sleep log data -Review recommendations for optimal sleep hygiene -Review tasks to be completed for next session (continue sleep log completion and review sleep hygiene recommendations)
2	
 -Conceptualize OSA as a multidimensional problem -Identify cognitive, emotional, reciprocal influences, and environmental factors affecting couples' functioning -Discuss cognitive distortions and communication -Improve adaptive coping through improving self-efficacy and working with cognitive distortions such as maximization and catastrophizing -Benefit finding -Relapse prevention -Consolidate skills

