Patient demographic and medical characteristics (e.g., comorbid conditions) will be obtained directly from EpicCare. Socioeconomic status will be assessed by asking patients about their education, occupation, and income. Patient and bed partner relationship quality will be assessed using the 4-item version of the Dyadic Adjustment Scale (DAS-4), one of the most widely used measures of couple satisfaction in research and clinical practice.⁷⁶ The 6-item Zarit Burden Interview for Dementia Caregivers is one of the most widely used measures of caregiver burden.⁷⁷ OSA severity will be assessed using the apnea-hypopnea index, the time spent with oxyhemoglobin saturation < 90%, and the lowest value of oxyhemoglobin saturation each retrieved from the polysomnogram report.⁷⁸ All participants will be given an autotitrating CPAP machine that can be monitored remotely. The device will upload objective adherence data to RedCap each morning following use. **Adherence is the average nightly use of CPAP from baseline to designated follow-up times (30 days, 90 days).**

Instruments to measure OSA knowledge and beliefs, depression, sleepiness, quality of sleep, quality of life, self-efficacy to use CPAP, and degree of bed partner involvement in CPAP adherence will be completed by all study participants at **baseline, 30 days, and 90 days**. These instruments have demonstrated reliability and validity and have been used in previous

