9.0 Study Timelines

Participants will be enrolled from April 1, 2022 to December 31, 2022. Participants will participate in the study for 90 days. The estimated date for primary analysis to be completed will be March 1, 2023.

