13.0 Recruitment Methods

Prior to enrollment of the first subject, sealed envelopes containing participant computer-randomized study arm assignment will be created. To assure balanced but unpredictable assignments of participants we will use permuted block randomization, stratified by study site.^{88,89} Study flyers will be distributed to sleep providers to distribute to eligible patients who can contact study staff for enrollment. Research assistants will obtain automated digital reports from EpicCare of patients who have received an at-home or in-lab diagnostic sleep study over the previous 48 hours and an order for initiation of CPAP. They will review EpicCare to verify eligibility (see Table above). Study staff will mail a study brochure and consent form to patients. Those who do not respond within 72 hours will receive a phone call to confirm patient and bed partner eligibility and to explain the study in detail. Upon obtaining verbal confirmation, staff will arrange a date and time to meet with patients and their bed partners in person to obtain written consent and to administer baseline study instruments. After completion of these initial tasks, staff will open envelopes to determine subject study arm assignment. Only the sleep technologist, the research assistants who enroll the patients and the participants will be aware of study arm assignments. Participants will receive ClinCard payments within 1 week of completion of study tasks. Participants will receive \$50 for completion of the baseline, 30-day, and 90-day instruments (\$150 total / participant paid by ClinCard). Participants will also be reimbursed for public transportation or parking.

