17.0 Data Management and Confidentiality

Our study database will be stored in RedCap (<https://www.project-redcap.org>),⁹⁰ a secure, open-source software application regularly utilized by [name] research teams. RedCap runs on the MetroHealth server and therefore is HIPAA compliant, provides user-specific data access, and facilitates removal of participant identifying data prior to exporting. It also facilitates double data entry with real-time data validation and data integrity checks. Patient data will be entered directly into the RedCap. Study data will be held for 7 years following study completion. Paper records will be stored in locked filing cabinets within the Center for Reducing Health Disparities (Rammelkamp R209). Mosio will use HIPAA compliant procedures to securely send and receive data between study participants and RedCap.

Because this is a pilot study, a power calculation is not provided.

We will begin our analysis by computing descriptive statistics and using graphical representations to examine all predictor and outcome variables. For each study patient, the primary outcome will be CPAP adherence at 90 days as determined by the mean daily CPAP usage (the total number of hours of CPAP use divided by the number of days observed for the

individual). An intention to treat analytic approach will compare mean daily CPAP usage between intervention and control patients as randomized. Linear mixed effects models using random effects will be used to adjust for clustering of patients within sleep provider. Covariates (fixed effects) will include indicator variables for BMI, AHI, gender, and treatment.⁸⁹ The model assumption that the overall CPAP usage outcome is normally distributed will be tested using the Shapiro-Wilk test. If a significant departure from normality is obtained (and a suitable transformation, such as log, is not found) an alternative approach will be to use a generalized linear (e.g., Poisson regression) model for the overall adherence (CPAP usage rate). A Wald test (with robust estimate of standard error) will be used to test for an intervention effect and a corresponding 95% confidence interval for the intervention effect will be computed. If substantial variability in follow-up times are found (e.g., due to dropout and/or missed visits), a weighting approach (using weights proportional to the number of days observed for each individual in conjunction with the selected model) can be used.

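### The second of two peer support groups is set at 3 months, where the 90-day primary outcome closes, so read literally no primary-outcome night follows it

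*Protocol*

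**What the plan says.** Section 1.0 lists peer motivators among the research interventions, and Section 2.0 fixes the number of meetings: "Couples will participate in two couple-oriented support groups led by an African American patient". Section 5.02a sets their timing by reference to the control sessions: "the health-related virtual webinars at 1 and 3 months will be replaced by OSA virtual support groups led by an African American patient". Section 5.01 puts those control sessions "at 1 and 3 months led by African American physicians with expertise in each topic". The task table in Section 6.0 repeats that there are two sessions but gives no dates.

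The outcome is defined consistently as a running average. Section 4.0: "Primary Endpoint: Mean CPAP adherence over 90 days". Section 6.0: "Adherence is the average nightly use of CPAP from baseline to designated follow-up times (30 days, 90 days". Section 17.0 computes it as "the total number of hours of CPAP use divided by the number of days observed". Section 9.0 closes follow-up at the same point: "Participants will participate in the study for 90 days". Questionnaires are also due then; Section 13.0 pays for "completion of the baseline, 30-day, and 90-day instruments".

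No section gives an earlier date or a window for the second support group, or says from which event the months are counted.

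**The concern.** A cumulative mean can reflect a session only through the nights that come after it. If the second support group is held when the averaging window closes, it is delivered and paid for but cannot register in the outcome by which the package is judged. Someone reading the 90-day result would credit or fault two peer sessions when only one had the chance to act. Section 2.10 presents peer motivators as one of the features that set this trial apart, and participants meet them only in these two groups. The schedule of an intervention belongs in the protocol, so a statistical analysis plan would not be expected to settle it.

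**Working it through.** The protocol states no figure to reproduce; this is a day count.

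**Inputs.** Outcome window of 90 nights (Sections 4.0, 6.0, 17.0). Support groups at 1 and 3 months (Sections 5.01, 5.02a). Enrolment from 1 April to 31 December 2022 (Section 9.0). CPAP supplied at enrolment (Section 6.0) or within a week of it (Section 5.01), so a lag L of 0 to 7 days. Twenty couples, half per arm (Section 2.0).

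**Step 1: three months in days.** Over all 275 enrolment dates, adding three calendar months gives day 90 for 32 dates, day 91 for 62 and day 92 for 181. None is earlier than day 90. For 62 + 181 = 243 of 275 dates (88%) the session falls after the 90-day participation period.

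**Step 2: nights left.** Count days from enrolment. Outcome nights run from day L to day L + 89. After a session on day D there remain L + 90 − D nights if the night of the session counts, one fewer if it does not, and never less than 0.

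| Reading of the second session | D | L | Nights after, of 90 |
|---|---|---|---|
| Literal | 90–92 | 0 | 0 |
| 3 months means 12 weeks (assumption) | 84 | 0 | 5–6 |
| CPAP starts 7 days after enrolment (assumption) | 90–92 | 7 | 4–7 |
| Session held two weeks early (assumption) | 76–78 | 0 | 11–14 |
| Both of the last two (assumption) | 76–78 | 7 | 18–21 |
| Earliest day of the third month (assumption) | 61 | 0 | 28–29 |

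The looser readings therefore run from about 4 to 29 nights, at most 29/90 = 32%. For comparison, the first session at day 30 leaves 90 − 30 = 60 nights (67%).

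**Step 3: an earlier second session.** Counting from CPAP receipt (L = 0): day 45 leaves 45 nights (50%), day 60 leaves 30 (33%) and day 75 leaves 15 (17%), or one fewer each if the night of the session is excluded.

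**Step 4: what a night is worth.** If a session raised use by g hours on each of n later nights, the 90-day mean would move by g × n/90. The documents give no effect for a peer session. Taking g = 1 purely as an illustration, the mean moves by 0 h for n = 0, 0.17 h (10 minutes) for n = 15, 0.33 h (20 minutes) for n = 30 and 0.50 h (30 minutes) for n = 45.

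**Step 5: can groups be formed?** Ten couples per arm over 9 months, accrued evenly (assumption), is 10/9 = 1.11 per arm per month. A 15-day window such as day 53–67 holds 15 × 1.11/30.4 = 0.55 couples. A 31-day window such as day 45–75 holds 31 × 1.11/30.4 = 1.13. Pooling three couples takes 3/1.11 = 2.7 months of accrual.

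**The case against.** The best reply is that three months is a nominal label. These are group meetings in a trial that enrols over nine months, so they cannot land on each couple's exact day 90 unless held for one couple at a time. Counting individual dates gives the schedule a precision the protocol never claims. This stands in part: the literal count is one reading, and the others leave some nights. But the text places the sessions at those months, and nothing in it requires the second to be earlier.

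It is also fair to say that the harm is limited. Control webinars follow the same timetable, so contact is matched. Couple education, text messages, telemonitoring and couple therapy are untouched, and the first support group acts on most of the window. This is a pilot without a power calculation. All of that stands and keeps the severity down.

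Three stronger inferences are tempting, and the documents do not support them:

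- **The 90-day result reflects a package with one support group.** That follows only if the unanchored label is taken literally.
- **The 90-day questionnaires cannot be affected either.** The protocol does not order them against the second session. They are measures at a point in time, so a session held shortly before could still influence them.
- **The treatment comparison is biased.** Late delivery weakens what is being compared; it does not undermine the randomization.

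Finally, month 2 is not prescribed anywhere in the protocol, and a tight window would often contain a single couple. That is a sound argument for a wide window. It does not justify leaving the session at the close of follow-up.

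**Conclusion.** The point holds as a scheduling weakness. Following the plan as written leaves 0 of 90 primary-outcome nights after the second support group; looser readings leave about 4 to 29, each resting on an assumption about the label, the CPAP start or an early session. One component of the intervention is diluted by an amount that cannot be put in hours without an assumed effect per session. The peer component as a whole still bears on the primary outcome through the first session. Severity is low to moderate, and the case for changing it rests mainly on how little the change costs.

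**What to change.** In Section 5.02a, schedule the second support group at about two months after CPAP receipt, and name that starting event. Give it a window wide enough to assemble groups but closing well before day 90. Day 45 to 75 would leave about 15 to 45 of the 90 nights. State that the session comes before the 90-day instruments. In Section 5.01, move the second control webinar to the same window so that contact stays matched between arms.

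This needs wording in two sections and the rescheduling of virtual sessions already planned. It adds no sessions, staff or participants, and participation stays at 90 days. The downside is tighter scheduling and small groups: under even accrual (assumption) even the wider window holds only about one couple per arm at a time, so the sponsor should accept meetings of one or two couples with the peer leaders.
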